Prior to a subject undergoing surgery of an adnexal mass, a baseline grayscale scan of the lesion will be obtained, while power Doppler imaging (PDI) will be performed to select the area with the greatest vascularity. Two contrast injections will be administered. The first injection will involve pulse inversion grayscale EV SHI of the area of greatest vascularity within the adnexal mass (established by baseline PDI). There will be a 15 minute pause between injections to allow for complete contrast clearance. For the second injection, Definity will be infused over 5 minutes and subharmonic destruction/reperfusion SHI imaging performed in multiple imaging planes covering the adnexal mass.

The pre- and then post-contrast US imaging will be read independently by the 2 experienced co-investigators blinded to the surgical results and contrast-enhanced MRI evaluations. Then, sensitivity, specificity and accuracy will be calculated for all imaging modalities (baseline and SHI as well as MRI) and compared to the RMI used to select patients for surgery [Ferrazzi et al. 1997; 2005; Moolthiya & Yuenyao 2009]. Off-line SHI time intensity curves (TICs) will be created on a pixel by pixel basis and TIC parameters will be compared to the lesion characterization by the other imaging modalities with pathology as the reference standard. Finally, the ability of EV SHI to image angiogenesis (specifically fractional tumor vascularity) will be compared to so called “hot spots” within surgical specimens stained for an immunohistochemical predictor of angiogenesis (the endothelial cell marker CD31).

Statistical Methodology: As this project involves a pilot study of a new US imaging mode (SHI) in a completely new application, no power analysis can be performed *a priori*. Nonetheless, our statistical analysis will address the following two major questions:

1. Can EV SHI biomarkers improve the characterization of benign and malignant adnexal masses compared to standard US or contrast enhanced MRI or other parameters?
2. Do SHI ovarian neovascularity measurements correlate with iMVD as a marker of angiogenesis?

As a pilot study this project is not powered to provide definitive answers to the questions presented above, but rather is a first step towards establishing feasibility and to provide data for a future more exhaustive study.

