1.1 Background

Among the early changes that differentiate normal from cancerous tissues is the process by which the tumor develops its blood supply, tumor angiogenesis [Folkman 1990; Li 2000]. In addition, angiogenic vascular morphology, often quantified as the intra-tumoral microvessel density (iMVD), is an independent predictor of malignant disease; including in the ovaries [Brawer et al. 1992; Labiche et al. 2009; Palmer et al. 2007; Weidner et al. 1991; Weind et al. 1998; Wang et al. 2011]. Angiogenesis is a prerequisite for tumor growth greater than 2 mm³ and is also a key factor of metastasis by allowing the ingrowth of vessels into a tumor providing a pathway for systemic dissemination via the blood or lymph system [Holmgren et al. 1995; O'Reilly et al. 1994]. Therefore, tumor angiogenesis is an important marker for imaging adnexal masses. The opportunity for noninvasive imaging of tumor angiogenesis is strengthened by the fact that vessels

form a substantial portion of the mass of malignant tumors, contributing up to 10 % of the total volume of the tumor [Jain 1994]. Currently adnexal masses are imaged with standard EV US, with contrast enhanced MRI or computed tomography (CT) as well as, more rarely, with positron emission tomography (PET) [Bazot et al. 2008; Fleischer et al. 2012; Mohaghegh & Rockall 2012; Moyle et al. 2010]. While overall accuracies of 88 to 93 % have been reported for the latter modalities [Bazot et al. 2008; Mohaghegh & Rockall 2012], they are quite expensive and employ contrast agents which can produce marked adverse reactions, while CT also exposes patients to significant radiation.

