2. TRIAL OBJECTIVES

Trial Objectives: The primary objective of this trial is:

- To develop qualitative subharmonic imaging (SHI) or SHI-derived quantitative biomarkers and **to generate pilot data for a study to evaluate if they improve the characterization of benign and malignant adnexal masses compared to standard ultrasound or contrast enhanced magnetic resonance imaging (MRI) or the risk of malignancy index (RMI).**

and a secondary objective is:

- To compare the SHI depiction of adnexal masses' neovascularity in humans to intra-tumoral microvascular density (iMVD) obtained from CD31 an immunohistochemical marker of angiogenesis.

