6.4 Efficacy Assessments

The pre- and then post-contrast ultrasound imaging will be evaluated for each patient as follows: grayscale, grayscale and PDI (baseline), and grayscale and SHI. While this may introduced some bias from pre- to post-contrast results, we considered this the more realistic approach to how CEUS may be used in clinical practice. Each case will be read independently by the 2 experienced co-investigators (15+ years of expertise in CEUS imaging) blinded to the surgical results and contrast-enhanced MRI evaluations, to allow repeatability to be assessed. All ultrasound studies will be rated on a quasi-continuous scale from 0 to 100 ranging from “no lesion seen (no findings)” over “definitely benign,” “indeterminate” to “definitely malignant.” Using a quasi-continuous 100-point rating scale has an intuitive probabilistic interpretation and is known to improve the assessment of the capabilities of the imaging modes studied [Wagner et al. 2001]. The SHI clips will be processed to produce CMI-SHI images [Dave & Forsberg 2009; Dave et al 2010], which will also be read by the blinded readers. Finally, sensitivity, specificity and accuracy will be calculated for all imaging modalities (baseline and SHI as well as MRI) and compared to the RMI values used to select patients for surgery [Ferrazzi et al. 1997; 2005; Moolthiya & Yuenyao 2009].

Off-line SHI TICs will be created on a pixel by pixel basis. Parametric images will be generated showing time-to-peak, perfusion rate, peak intensity (calculated in dB as the ratio of the peak to the baseline values) and area under the curve (AUC) in the area of greatest vascularity as well as parameters across the mass (based on the data from second infusion) [Eisenbrey et al. 2011b]. The TIC parameters will be compared to the lesion characterization of the other imaging modalities with pathology as the reference standard. It is our hypothesis that these new SHI based biomarkers will improve our capabilities to characterize ovarian cancers. Results will also be compared to MRI enhancement kinetics and imaging assessments obtained as part of the subjects’ standard of care.

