7.2 Statistical Analyses

7.2.1 Hypotheses

H₁: EV SHI will significantly differentiate malignant from benign adnexal masses using surgical pathology as the reference standard. As an initial end-point we speculate that an area under the ROC curve of 0.75 or better will be achieved by EV SHI.

H₂: EV SHI biomarkers will improve the characterization of benign and malignant adnexal masses compared to standard ultrasound or contrast enhanced MRI or other clinical parameters. As an initial end-point we speculate that an area under the ROC curve of 0.75 or better will be achieved by EV SHI, which will be better than low-end estimates of the accuracy of standard ultrasound, contrast enhanced MRI and other clinical parameters (which is on the order of 0.70 to 0.72).

H₃: A correlation coefficient of 0.70 will be achieved between *in vivo* SHI ovarian neovascularity measurements and iMVD.

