7.2.3 Sample Size Considerations

As this project involves a pilot study of a new ultrasound imaging mode (i.e., SHI) in a completely new application, no power analysis can be performed *a priori*. As a pilot study this project is not powered to

provide definitive answers to the hypotheses presented above (cf., section 7.2.1), but rather is a first step towards establishing feasibility and to provide data for a future more exhaustive study. The planned sample size of 45 subjects will provide important information on the precision of the anticipated correlation coefficient of 0.70 between in vivo SHI ovarian neovascularity measurements and iMVD such that the 95% confidence interval would be (0.51, 0.82).

The Gynecological Oncology Division at TJU evaluate more than 500 women with adnexal masses each year out of which around 1 woman/week will require surgical intervention based on their morphological characteristics (on standard imaging), CA125 levels and menopausal status [Ferrazzi et al. 1997; 2005; Moolthiya & Yuenyao 2009]. The patient population of this project will reflect the population demographics found at major American urban academic health centers. The overall hospital demographics for TJU include 60 % Caucasian, 16 % African American, 13 % Hispanic, 5 % Asian, 1 % Other, and 5 % unknown patients. We anticipate enrolling approximately 45 subjects scheduled for surgery in this project (with some 15-20 % expected to be cancers), which means we are aiming for a recruitment rate of approximately 58% (45/78).

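### H2 claims improvement over other tests, but its end-point is H1's AUC of 0.75 set against a fixed 0.70 to 0.72, so it can be met without improvement; the AUC also has no stated precision

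*Combined protocol and SAP*

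**What the plan says.** The primary objective (section 2) is to develop SHI measures and to "generate pilot data for a study to evaluate if they improve the characterization of benign and malignant adnexal masses", compared with standard ultrasound, MRI or the risk of malignancy index (RMI). The secondary objective concerns agreement with microvascular density.

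In section 7.2.1, H1 says SHI separates malignant from benign masses. H2 says SHI biomarkers do so better than the other tests. Both carry the same sentence: "As an initial end-point we speculate that an area under the ROC curve of 0.75 or better will be achieved by EV SHI". H2 adds only that this is a value "which will be better than low-end estimates of the accuracy of standard ultrasound, contrast enhanced MRI and other clinical parameters", on the order of 0.70 to 0.72. No source is given for that figure, and the text does not say whether it is an AUC or a proportion correct.

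Section 7.2.2 compares the imaging tests by ROC analysis, uses logistic regression for incremental value over RMI and morphology, and tests differences between ROC curves with Mann-Whitney statistics. H2's end-point does not refer to this analysis.

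Section 7.2.3 states that the pilot is not powered for the hypotheses. It says that 45 subjects will give "important information on the precision of the anticipated correlation coefficient of 0.70", with a 95% interval of 0.51 to 0.82. It anticipates about 45 women, "with some 15-20 % expected to be cancers". It gives no interval for an AUC.

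**The concern.** A hypothesis of improvement needs a quantity that can show improvement. H2's end-point holds the comparators at a constant, so it is reached exactly when H1's is reached and says nothing further. SHI could reach 0.75 while MRI or RMI does better in the same women. The end-point and the ROC comparison in 7.2.2 would then point in opposite directions, and the plan does not say which one answers H2.

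The benchmark is also unclear. Its decimal form, set beside an AUC, suggests that it is an AUC. Yet the Synopsis and section 6.4 use accuracy for a measure listed beside sensitivity and specificity ("sensitivity, specificity and accuracy will be calculated for all imaging modalities"), which suggests proportion correct.

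Finally, the only prospective precision figure belongs to the secondary objective. The AUC serves the primary objective and has none, although all the inputs needed for one are stated.

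**Working it through.** **Inputs from the plan.** AUC 0.75 and benchmark 0.70 to 0.72 (7.2.1); 45 subjects and 15 to 20% cancers (7.2.3). 45 × 0.15 = 6.75 and 45 × 0.20 = 9, so 7, 8 or 9 cancers against 38, 37 or 36 benign masses.

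**Assumptions not in the plan.** One mass per woman; all 45 evaluable on both tests; Hanley-McNeil variance; equal-variance binormal ratings in the simulation; correlation between the two AUC estimates of 0 to 0.7.

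**1. The plan's own figure.** Fisher z for r = 0.70, n = 45: atanh(0.70) = 0.867 and 1.96/√42 = 0.302. Back-transforming 0.867 ± 0.302 gives 0.51 to 0.82, as printed.

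**2. Precision of an AUC of 0.75.** With m cancers and n benign masses,

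SE² = [A(1−A) + (m−1)(q1−A²) + (n−1)(q2−A²)] / (mn), where q1 = A/(2−A) = 0.600 and q2 = 2A²/(1+A) = 0.643.

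For m = 7, n = 38: (0.1875 + 0.2250 + 2.9732)/266 = 0.01273, so SE = 0.113. For m = 9, n = 36: (0.1875 + 0.3000 + 2.8125)/324 = 0.01019, so SE = 0.101.

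| Cancers / benign | SE | Wald 95% interval | Logit 95% interval |
|---|---|---|---|
| 7 / 38 | 0.113 | 0.53 to 0.97 | 0.48 to 0.91 |
| 8 / 37 | 0.106 | 0.54 to 0.96 | 0.50 to 0.90 |
| 9 / 36 | 0.101 | 0.55 to 0.95 | 0.51 to 0.90 |

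Every interval contains 0.70 to 0.72. The method matters near 0.5: with 7 cancers the logit interval includes 0.5 and the Wald interval does not.

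**3. How often the H2 end-point is reached** (observed SHI AUC of at least 0.75; 100,000 simulated trials per cell):

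| True SHI AUC | 7 cancers | 8 cancers | 9 cancers |
|---|---|---|---|
| 0.70 | 34% | 33% | 33% |
| 0.72 | 41% | 41% | 40% |
| 0.75 | 53% | 53% | 53% |

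The comparators' true AUC does not affect these rates, because the end-point does not use it.

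**4. Can the end-point and the ROC comparison disagree?** Take SHI's true AUC as 0.75, a comparator's as 0.80 (assumed), and a rating correlation of 0.5 (20,000 trials). The end-point is still met in about 53% of trials. In 56 to 58% of those, the comparator's observed AUC is at least as high as SHI's.

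**5. Precision of the within-patient difference.** SE(diff) = √(s1² + s2² − 2ρ·s1·s2), for 0.75 against 0.70 or 0.72.
- For ρ = 0.7 down to 0.3, the 95% half-width is 0.16 (9 cancers) to 0.27 (7 cancers). At ρ = 0 it reaches 0.32.
- The implied gain is 0.75 − 0.72 = 0.03 to 0.75 − 0.70 = 0.05.
- With a gain of 0.05, ρ = 0.7 and 9 cancers, the interval is −0.11 to 0.21. With a gain of 0.03, ρ = 0.3 and 7 cancers, it is −0.24 to 0.30.

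**6. If the benchmark means proportion correct.** Calling every mass benign is correct in 36/45 = 80.0% to 38/45 = 84.4% of women and has an AUC of 0.5. This shows only that the two scales cannot be ranked against each other. It says nothing about how good the comparators are.

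**The case against.** The best defence is that the comparison is already planned. Section 7.2.2 compares ROC curves within the study and cites the standard method for correlated curves. A reader might infer from H2 that the trial compares SHI with a constant only, and the documents do not support that. What stands is narrower: the sentence offered as H2's end-point is not linked to that analysis and can disagree with it.

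Second, the plan only speculates about an initial end-point, no decision depends on 0.75, and the Synopsis and 7.2.3 disclaim definitive answers. This is fair. The rates in step 3 describe a threshold that triggers nothing, and their independence from the comparators is true by construction. Nor is the wide interval a fault in itself, since the plan declares that it is unpowered. The disclaimer does not explain why precision is given for the correlation and not for the AUC.

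Third, a reader might infer that section 1.1 contradicts the benchmark, because "overall accuracies of 88 to 93 % have been reported for the latter modalities" in a passage that names MRI, CT and PET. That is not shown. The conflict exists only if 0.70 to 0.72 means proportion correct for MRI, which is the less likely reading. H2 also speaks of low-end estimates, which may sit below other published figures. It is a point to clarify.

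Fourth, a future study would probably be planned from the AUCs and differences observed here rather than from the benchmark. This limits the harm.

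**Conclusion.** The point holds, at minor to moderate severity. As written, H2's end-point does not measure what H2 claims. It repeats H1's threshold against a fixed figure with no metric or source, and it can be met without improvement: in about 33 to 41% of trials at a true SHI AUC of 0.70 to 0.72 and about 53% at 0.75, whatever the comparators achieve. Section 7.2.3 also omits the precision of the AUC that serves the primary objective.

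The figures rest on 7 to 9 cancers, binormal ratings and all 45 women being evaluable on both tests; fewer evaluable pairs would widen the intervals. The paired half-widths also depend on an assumed correlation that the documents do not give. The finding does not extend to a claim that the in-study comparison is missing, that the pilot should have been powered, or that the benchmark contradicts the Background.

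**What to change.** 1. In 7.2.1, restate the H2 end-point as the within-patient difference, AUC(SHI) minus AUC(comparator), separately for standard ultrasound, MRI and RMI. Estimate each with a 95% interval (DeLong or bootstrap) from the ROC comparison already planned in 7.2.2. Keep 0.75 as H1's end-point only.
2. Delete 0.70 to 0.72, or restate it as a sourced AUC used as background only. If it is kept, say how the MRI figure relates to the accuracies in section 1.1.
3. In 7.2.3, beside the H3 interval, add the expected 95% interval for an AUC of 0.75 with 7 to 9 cancers and name the method: Hanley-McNeil Wald 0.53 to 0.97 narrowing to 0.55 to 0.95, or logit 0.48 to 0.91 narrowing to 0.51 to 0.90. Add the paired-difference half-width: about 0.16 to 0.27 at an assumed correlation of 0.3 to 0.7, and up to 0.32 at 0. State that all 45 are assumed evaluable on both tests.

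The cost is a few sentences and an interval on an analysis already planned, with no extra patients. The downside is that the stated end-point becomes less favourable, and the paired interval will probably include zero.

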7.2.2 Analysis of Results

The findings of SHI will be correlated to vascular morphology (i.e., tumor angiogenesis ascertained with CD31) and other imaging and pathological findings; including size, vascularity, presence or absence of receptors and RMI values. The techniques will be compared using an analysis of variance (ANOVA) with method (i.e., baseline ultrasound imaging, SHI, or MRI) as the dependent variable and outcome as the independent variables. For the pre and post-contrast enhanced comparisons, dichotomous parameters (e.g., benign/malignant) and ranked data (less, iso, or more intense) will be analyzed with the McNemar test. The ability of the imaging tests to distinguish benign from malignant masses will be compared using ROC analysis, while the incremental validity of imaging diagnosis and morphological characteristics as well as serum biomarkers (i.e., RMI) will be analyzed using logistic regression and ROC analyses [DeLong et al. 1988; Metz 1986; Wagner et al. 2001]. Differences between ROC curves will be tested by computing Mann-Whitney statistics. All of the statistical analyses proposed for this human clinical trial will be repeated split by racial and ethnic groups to determine if clinically important race/ethnicity differences exist in the ability of SHI to characterize adnexal masses (although the limited sample size of this pilot study makes it unlikely that such differences – if any exist - will be detectable).

All analyses and computations will be performed using NCSS/PASS 2008 and Stata 12.0 (Stata Corporation, College Station, TX), while the study database will be designed and implemented in REDCap (Vanderbilt University, Nashville, TN). This database will contain all patient information (except names and other identifiers), including pathology, MRI and SHI measurements as well as other clinical variables.

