6.3.2 Ultrasound Imaging

The ultrasound examinations will be performed by a qualified sonographer. Procedures and equipment for this trial will be used in accordance with typical clinical procedures. All trial procedures will be conducted in accordance with Good Clinical Practice. A modified Logiq E9 scanner with a [REDACTED] C10-3v EV transducer

(GE Healthcare) operating in SHI mode will be used to obtain subharmonic radiofrequency (RF) data from the adnexal mass within the ovary and/or fallopian tube. Both the experimental machine and software will be labeled as an investigational device with a GE provided label prior to beginning any clinical experiments (21 CFR 812.5).

A baseline grayscale ultrasound scan of the lesion will be obtained and the following criteria assessed: the size, shape, and orientation of the site; echogenicity compared to surrounding tissue. Standard PDI of the mass will also be performed to select the area with the greatest vascularity. The distribution of color signals and the overall color content of the mass will be evaluated by comparing the pattern and amount of color to normal tissue on the contra-lateral side. If uniform, the color will be categorized as less intense, iso-intense or more intense than normal tissues. If non-uniform, the color will be described by location, intensity and distribution. Anastomoses between adjacent vessels will be noted (as 1-2, 3-5 or >5 vessels connecting). The vascular pattern will also be graded as peripheral, radial, spotty or a combination. Digital clips of the two baseline imaging modes will be acquired.

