Two contrast injections will be performed. The first injection will involve pulse inversion grayscale EV SHI (in a dual display format utilizing at a transmit frequency of 5.8 MHz and the subharmonic obtained at 2.9 MHz [Eisenbrey et al. 2011a; Sridharan et al. 2015]) of the area of greatest vascularity within the adnexal mass (as established by baseline PDI) followed by IV administration of 1.3 to 1.5 ml of Definity and acquisition of the contrast enhancement covering baseline, wash-in and peak enhancement to complete wash-out (typically 1-2 minutes). There will be a 15 minute pause between injections to allow for complete contrast clearance. For the second injection, we will infuse up to 1.5 ml of Definity mixed in 25 ml of saline over 5 minutes and then perform subharmonic destruction/reperfusion SHI imaging in multiple imaging planes covering the adnexal mass through the entire period of enhancement (in practice 3-4 minutes of equilibrium contrast concentration); similar to our previous work [Linden et al. 2007; Shi et al. 2001]. The digital clip(s) obtained from the SHI injection will be transferred to a PC for off-line analysis. The SHI images will be qualitatively analyzed as described above. It should be noted, that all subjects will be

closely monitored by a physician during the study [FDA Alert 2007; 2008].

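### Two test specifications in section 7.2.2 are wrong as written: the ANOVA takes imaging method as its dependent variable and names no patient term, and McNemar is assigned to a three-level grade

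*Combined protocol and SAP*

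**What the plan says.** To set the techniques against each other, section 7.2.2 (Analysis of Results) specifies this model: "analysis of variance (ANOVA) with method (i.e., baseline ultrasound imaging, SHI, or MRI) as the dependent variable and outcome as the independent variables". Outcome is not defined there, and no patient, block or reader term is named. For comparisons before and after contrast, the same section says that "dichotomous parameters (e.g., benign/malignant) and ranked data (less, iso, or more intense) will be analyzed with the McNemar test". Discrimination is handled separately: "The ability of the imaging tests to distinguish benign from malignant masses will be compared using ROC analysis".

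The data are paired. Under section 6.4 the ultrasound imaging "will be evaluated for each patient as follows: grayscale, grayscale and PDI (baseline), and grayscale and SHI", and two readers read each case independently. The rating is defined for ultrasound: "All ultrasound studies will be rated on a quasi-continuous scale from 0 to 100". MRI comes from standard of care, and the inclusion criteria in section 4.1 do not require it.

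The three-level grade comes from the power Doppler description in section 6.3.2: "If uniform, the color will be categorized as less intense, iso-intense or more intense than normal tissues". Other masses are described instead: "If non-uniform, the color will be described by location, intensity and distribution". For contrast imaging, the same section says "The SHI images will be qualitatively analyzed as described above".

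**The concern.** An ANOVA needs a measured response. Baseline ultrasound, SHI and MRI are labels that the design assigns, so modelling them as the response tests nothing about the techniques. Reversing the roles completes only half the repair: readings from one woman are correlated, and the text does not say whether the model links them.

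McNemar compares the two discordant cells of a paired 2x2 table. A less, iso or more intense grade gives a 3x3 table with six off-diagonal cells, so the test is undefined until levels are merged or an extension is named. Section 7.2.2 also does not say what happens to masses whose colour is not uniform.

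The analyst would therefore have to guess the ANOVA response, the handling of pairing, and how three levels become a McNemar table. The results are meant as pilot data for a later study, and section 7.2.2 repeats every analysis by race and ethnicity, so the guesses carry through.

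**Working it through.** **The plan's own figure.** Neither test carries a power or precision figure. The only computed precision in the plan is the interval in section 7.2.3 for a correlation of 0.70 with 45 subjects. Fisher's z gives atanh(0.70) = 0.867 and 1.96/sqrt(45 - 3) = 0.302, so the limits are tanh(0.565) = 0.512 and tanh(1.170) = 0.824. The stated (0.51, 0.82) is reproduced and does not depend on this point.

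**ANOVA run literally.** Suppose every woman has all three methods.
- If outcome is pathology, each label occurs equally often among benign and malignant masses. The mean of the coded labels is then the same in both groups, so F = 0 and p = 1 whatever the images show.
- If outcome is a reading, the answer depends on the arbitrary coding of the labels. One simulated data set, with readings dichotomised, gave p = 1.00 with ultrasound = 1, SHI = 2, MRI = 3, and p = 0.048 with ultrasound = 1, MRI = 2, SHI = 3.

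**Roles corrected, pairing ignored.** Inputs: 45 women (section 7.2.3); the three ultrasound modes of section 6.4; one reader; 7 or 9 cancers, since 45 x 0.15 = 6.75 and 45 x 0.20 = 9. The within-woman correlation rho is not in the documents; 0.3, 0.5 and 0.7 are assumed, equal for all pairs of modes.
- The true variance of a mode difference is proportional to 1 - rho, but the unpaired model uses 1. The standard error is too large by 1/sqrt(1 - rho) = 1.20, 1.41, 1.83.
- Simulated null rejection of the nominal 5% mode test (20,000 trials): about 1.6%, 0.3%, under 0.1%.
- Power in a separate simulation with one of three methods shifted by an assumed 0.4 SD: 0.44, 0.41, 0.36 without a patient term, against 0.63, 0.78, 0.95 with patient as a block.

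**Both readers in one model.** Assume 45 women, three modes, two readers, total variance 1, patient variance 0.5 and no mode effect. Let the patient-by-mode variance be 0, 0.125 or 0.25. With a patient intercept alone, the nominal 5% mode test rejects about 5%, 10% and 15% of the time (two simulations put the last at 15% and 17%). With a patient-by-mode term it rejects about 5% throughout. The reason is that both readers read the same images, so their two readings of one mode in one woman are not independent.

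**McNemar on three levels.** Hypothetical counts: 8 masses move from less to iso and 0 back; 2 move from iso to more and 4 back; none moves two steps.

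| Choice | Comparison | p |
|---|---|---|
| McNemar, less v rest | 8 v 0, exact: 2 x 0.5^8 | 0.008 |
| McNemar, rest v more | 2 v 4, exact: 44/64 | 0.69 |
| Stuart-Maxwell | 8.667, 2 df | 0.013 |
| Bowker | 8.667, 3 df | 0.034 |
| Exact signed-rank | 10 up v 4 down | 0.18 |

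The statistic 8.667 is 8²/8 + 2²/6. Omitting the empty less-more pair gives Bowker 2 df and p = 0.013, so its difference from Stuart-Maxwell here is only a convention on degrees of freedom. The signed-rank test equals the sign test because every move is one step.

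**The case against.** Much of the defence stands. The reversed roles look like a drafting slip, since the sentence sets out to compare techniques. The missing patient term is an omission from a one-sentence description; the plan nowhere chooses to ignore pairing. Extensions of McNemar to more than two levels exist, and a competent analyst would probably find one. The simulations use three ultrasound modes, whereas the planned ANOVA names baseline ultrasound, SHI and MRI. The 3x3 table was constructed so that the splits diverge; it shows that the choice can matter, not that it will. The pilot disclaims definitive answers. None of this supplies the missing specification, and no other section corrects either sentence.

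Stronger readings are tempting, but the documents do not support them:
- A reader might infer that ignoring the pairing produces false positives when methods are compared. It does the opposite. Rejection is inflated (about 12% to 21% in the same setting) only for a pathology effect averaged over modes, which no hypothesis in section 7.2.1 asks about.
- A reader might infer that McNemar is wrong throughout. For paired benign/malignant calls it validly tests a change in the call rate.
- A reader might take it as settled that the colour grade applies to SHI. That is the likely meaning of "The SHI images will be qualitatively analyzed as described above", but the section does not say how a Doppler colour grade transfers to grayscale SHI.

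**Conclusion.** Minor, and wrong as written on two counts: a design label is named as the ANOVA response with no patient term, and a paired 2x2 test is assigned to three ordered levels. If only the roles are corrected, the mode test is too strict, with true size about 1.6%, 0.3% or under 0.1% at assumed correlations 0.3, 0.5 or 0.7, and power is lost. For the grade, the unstated choice can decide the result, as the hypothetical p-values of 0.008 and 0.69 show; they do not estimate any effect in this trial.

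A reader might infer that the main hypotheses are compromised. They are not: H1 and H2 rest on the ROC analyses, H3 on a correlation, and the sample-size figures use neither test. Sensitivity, specificity and accuracy are also planned separately in section 6.4. Testing paired differences in sensitivity and specificity would be an optional addition and is not part of this error.

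**What to change.** Rewrite two sentences in section 7.2.2 before analysis.

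1. **ANOVA.** For the ultrasound modes, make the 0 to 100 rating the response, mode a within-patient factor and patient a random or repeated effect. Either fit each reader separately, or include both readers with a patient-by-mode random term; a patient intercept alone would make the mode test too lenient. Keep the planned ROC comparison as the test of discrimination. Compare MRI with ultrasound on correctness against pathology, in women who have an MRI.
2. **Three-level grade.** Name one paired test in advance: exact Wilcoxon signed-rank if the question is a net shift, or Stuart-Maxwell if it is any change in distribution. Apply it to masses graded uniform both before and after contrast, show the 3x3 table, and report how many masses are left out. State explicitly whether and how the colour grade applies to SHI. Keep McNemar for two-level items.

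The cost is some drafting, a mixed model and one paired ordinal test, with no new data. The downsides are that MRI leaves the three-method ANOVA and is compared only in women who had one, and that non-uniform masses leave the grade comparison.
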